Part 2 of this study will assess the safety, tolerability, PK and pharmacodynamics of inhaled MK-5475. Three additional panels of participants (Panels B, C and D) will be enrolled into Part 2. Participants in Panel B (N=4), C (N= up to 8) and D (N= up to 7) will participate in up to 3 dosing periods. Period 1 of Panel B will be an open label assessment of, safety/tolerability and PK, where participants will receive MK-5475. A review of available safety data up to 24 hours post dose and a rolling PK assessment will occur following completion of Panel B, Period 1, prior to going to the FRI period. Panel C, Period 1 will be an open label assessment of MK-5475. Panel C may begin once PK and safety data are reviewed from Panel B, Period 1. A rolling PK and safety data review of the first 4 participants of Panel C will occur prior to moving to the FRI period. The remaining participants in Panel C may enter Period 1 while this review is in progress. Following a review of individual safety along with a review of PK from first four participants in Panel C, the remaining participants will proceed to Period 2 (FRI period). The sample size of Panel C may increase based on number of participants from Panel A who do not continue into Part 2. Further enrollment of Panel C may end once screening of Panel D has begun. Panel D, Period 1 will be an open label safety/ tolerability and PK assessment of MK-5475. Following a review of individual safety of Period 1, participants will then proceed to Periods 2 (FRI period) and 3 (RHC period). The maximum sample size of Panel D is 7 but, may be less based on the final number of participants enrolled in Panel C and review of data from previous participants in Panel D. The total number of participants enrolled in Part 2 will be up to 24.

FRI Period

In Part 2, Period 2 for Panels B, C and D and Period 3 for Panel A, participants will undergo FRI. Participants will undergo a series of computed tomography (CT) scans to assess baseline and changes after dosing in pulmonary blood volume (PBV) through functional respiratory imaging (FRI) with an intravenous (IV) iodinated contrast agent.

RHC Period

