9.6 Statistical Methods

Primary (PVR): Fold change from baseline individual PVR in Part 2, RHC Period only will be calculated for each postdose time point. The largest reduction from baseline will be identified for each participant. These reductions will be natural log-transformed and mean and 95% confidence interval calculated based on a t-distribution at each dose-level. These will be exponentiated and expressed as percents to obtain the geometric mean and 95% CI for percent reduction in PVR.

Primary (Safety): Incidence of AEs will be descriptively summarized. Summary statistics and plots will be generated for the change from baseline values in the VS, ECG parameters, and selected laboratory safety parameters for participants, as deemed clinically appropriate. Depending on the safety parameter, the difference from baseline will either be computed on the original scale (raw change from baseline) or on the log scale and back-transformed for reporting (percent change from baseline). Summary statistics for the raw laboratory safety tests, ECGs, and/or VS may also be computed, as deemed clinically appropriate.

Secondary (HR and BP): Each of these parameters will be analyzed separately for Part 2, RHC period only. Individual PD parameters (HR, SBP, and DBP) will be natural log transformed and analyzed in a linear mixed effects model with fixed effects for dose, time (0.5, 4.5, and 24 hours), dose by time interaction and a random effect for participant. The dependent variable is: PD_postdose – PD_predose (PD=HR, SBP, DBP). An unstructured covariance matrix for each time point will be used to allow for unequal variances via the REPEATED statement in SAS PROC MIXED (a similar model would be acceptable using R) Kenward and Roger's method will be used to calculate the denominator degrees of freedom for the fixed effects (DDFM=KR). If the model fails to converge, a simpler covariance structure such as compound symmetry may be used. The difference in least squares means with 95% CI will be calculated for post dose of MK-5475 versus predose of MK-5475 at each dose level by time.

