Secondary (PK): Separately for each PK parameter (in Panel A, Part 1, Periods 1~3, and Panel B-D, Part 2, Period 1), individual values of AUC_{0-24hr} , $AUC_{0-\infty}$, C_{max} , C_{24} (as appropriate, if <50% C_{24} values are BLOQ) at each dose level will be natural log-transformed and evaluated with a linear mixed effects model containing a fixed effect for treatment and panel, and a random effect for participant. Kenward and Roger's method will be used to calculate the denominator degrees of freedom for the fixed effects. Ninety-five percent confidence intervals for the least squares means for each treatment will be

constructed on the natural log scale and will reference the t-distribution. Exponentiating the least-squares means and lower and upper limits of these confidence intervals will yield estimates for the population geometric means and confidence intervals about the geometric means on the original scale.

Secondary (PBV): Individual PBV will be natural log transformed and analyzed in a linear mixed effects model with fixed effects for dose, time, dose by time interaction and a random effect for subject. The dependent variable is: $\log(\text{PBV at X hour}) - \log(\text{PBV at 0 hour})$. An unstructured covariance matrix for each treatment will be used to allow for unequal variances and different correlations across time and treatment via the REPEATED statement in SAS PROC MIXED (a similar model would be acceptable using R) Kenward and Roger's method will be used to calculate the denominator degrees of freedom for the fixed effects (DDFM=KR). If the model fails to converge, a simpler covariance structure such as compound symmetry may be used. The difference in least squares means on the log scale will be calculated for MK-5475 postdose vs. predose at each time point (1, 3, 8 and 24 hours) at each dose level. These mean differences will be exponentiated to obtain the ratio of geometric means for PBV ($\text{MK_postdose} / \text{MK_predose}$) at each dose level.

Exploratory

The relationship between dose or plasma concentration and pharmacodynamic variables

PVR, pulmonary arterial pressure, cardiac output/cardiac index (CO/CI), systemic vascular resistance, mixed venous oxygen saturation and arterial oxygenation in participants with pulmonary arterial hypertension will be explored graphically. Upon visual inspection, additional model-based analysis might be employed to further explore the pharmacokinetic-pharmacodynamic relationship.

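### The PBV model adds a random subject effect that is redundant beside its unstructured covariance, and the only fallback it names, compound symmetry, gives up the unequal variances the plan asks for

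*Combined protocol and SAP*

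**What the plan says.** Section 9.6, Secondary (PBV), takes the log of PBV at each postdose time minus the log at predose and fits "fixed effects for dose, time, dose by time interaction and a random effect for subject". For the residuals it adds: "An unstructured covariance matrix for each treatment will be used to allow for unequal variances and different correlations across time and treatment". The model uses the REPEATED statement of PROC MIXED with Kenward-Roger degrees of freedom. Results are wanted "at each time point (1, 3, 8 and 24 hours) at each dose level" and are exponentiated to ratios of geometric means. The paragraph names no confidence interval. For trouble with the fit it says: "If the model fails to converge, a simpler covariance structure such as compound symmetry may be used".

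On the design, Section 4.1 states: "In Part 2, Period 2 for Panels B, C and D and Period 3 for Panel A, participants will undergo FRI". Table 1 (Section 1.2) gives the FRI dose as 240 µg in Panel A, 360 µg in Panels B and C, and 120 µg in Panel D.

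The HR and BP paragraph of Section 9.6 has the same random effect and the same fallback, at 0.5, 4.5 and 24 h, and does promise a 95% CI. Its covariance sentence reads: "An unstructured covariance matrix for each time point will be used to allow for unequal variances".

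**The concern.** A random subject effect together with a covariance matrix per treatment suits a crossover, where the random effect links one person's visits under different treatments. Here nobody has two FRI doses, so dose is a between-participant factor and there is nothing to link. A random intercept only adds one constant to every element of a matrix that is already free.

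Two things follow. The likelihood is flat in one direction, which can show up as non-convergence or a Hessian warning. Non-convergence is also the plan's only trigger for changing the covariance structure, and the one structure it mentions assumes a single variance at 1, 3, 8 and 24 h. A term that contributes nothing could therefore lead the analysis away from the unequal variances that the same paragraph sets out to allow. Any PBV intervals could then be too narrow at some times and too wide at others.

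**Working it through.** The plan gives no figure to reproduce for this model.

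**Step 1: count what can be identified.** Inputs: four postdose times and three FRI doses (Section 9.6; Table 1), and one vector of four changes per participant (Section 4.1). For a participant at dose *d* the marginal covariance is V_d = σ_b²·J + R_d, where J is a matrix of ones. A symmetric 4×4 matrix has 4×5/2 = 10 free elements; a 3×3 matrix has 3×4/2 = 6.

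| Structure | Parameters | Rank |
|---|---|---|
| PBV: unstructured by dose + random subject | 3×10 + 1 = 31 | 30 |
| PBV: common unstructured + random subject | 10 + 1 = 11 | 10 |
| PBV fallback: compound symmetry + random subject | 2 + 1 = 3 | 2 |
| HR/BP: unstructured over 3 times + random subject | 6 + 1 = 7 | 6 |

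Compound symmetry is itself σ_c²·J + σ²·I, so a random intercept is a second multiple of the same J. Without the random term, the PBV unstructured models have full rank (30 of 30, 10 of 10).

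**Step 2: what the redundancy does not affect.** On one simulated data set (24 participants, common matrix), σ_b² was moved through 0, 0.00046, 0.00092, 0.00138 and 0.00175 with R = V − σ_b²·J. At every value −2REML was −392.4076, and the standard errors of one dose's means at 1, 3, 8 and 24 h were 0.0195, 0.0188, 0.0207 and 0.0431. Only the split between σ_b² and R is undetermined. PROC MIXED itself was not run, so non-convergence is a possibility and has not been demonstrated.

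**Step 3: what homogeneous compound symmetry would do to intervals.** With complete data it estimates one variance, the average of the four time-specific variances. Relative to the correct width, the interval at time *t* is scaled by k_t = √(mean of σ²)/σ_t, and large-sample coverage is 2Φ(1.96·k_t) − 1. For SDs 1, 1, 1, 2: mean variance = (1+1+1+4)/4 = 1.75; k at 24 h = 1.323/2 = 0.661; coverage = 2Φ(1.296) − 1 = 0.805. At 1 to 8 h, k = 1.323 and coverage is 0.99.

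This was checked with 20,000 simulated trials per setting, using an assumed split of 8/10/6 over the three doses, complete data, and Satterthwaite degrees of freedom in place of Kenward-Roger. Coverage is for the group of 6, over correlations 0.3 and 0.6:

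| SD at 1, 3, 8, 24 h (assumed) | Formula, 24 h | Simulated, 1 h | Simulated, 24 h |
|---|---|---|---|
| 1, 1, 1, 1 | 0.950 | 0.950-0.951 | 0.949-0.950 |
| 1, 1, 1, 1.25 | 0.906 | 0.963-0.964 | 0.906-0.907 |
| 1, 1, 1, 1.5 | 0.866 | 0.975 | 0.865-0.867 |
| 1, 1.17, 1.33, 1.5 | 0.901 | 0.987 | 0.901 |
| 1, 1, 1, 2 | 0.805 | 0.990 | 0.803-0.805 |
| 1, 1.33, 1.67, 2 | 0.870 | 0.997 | 0.869-0.871 |

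A second simulation (split 7/6/11, correlation 0.6, 6,000 runs) gave about 0.91, 0.86-0.87 and 0.80-0.82 at 24 h for SD ratios 1.25, 1.5 and 2 when only the 24 h SD was raised. With a steady rise to the same ratios it gave about 0.92, 0.90 and 0.87. In the first simulation the unstructured model without the random effect covered 0.948 to 0.951 at every time under every pattern, whether common or by dose.

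**Step 4: HR/BP.** With the 24 h SD 1.5 times the other two: mean variance = (1+1+2.25)/3 = 1.417; k = 1.190/1.5 = 0.793; coverage = 0.88. Simulation gave 0.87-0.88.

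**Step 5: group size.** A by-dose 4×4 matrix is positive definite only if the dose group has n − 1 ≥ 4, so n ≥ 5. Panel D, the only 120 µg FRI group, has at most 7 participants and may have fewer (Section 4.1).

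**The case against.** The strongest reply is that little in the reported results depends on this. If the software sets the surplus variance to zero and converges, every mean and standard error is what it would have been without the random term. A reader might infer that the PBV effects cannot be estimated. Step 2 shows that they can.

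A reader might also infer that the plan commits the analyst to compound symmetry and to wrong intervals. It does not. The sentence is permissive and offers compound symmetry as an example, so a heterogeneous structure is already allowed. Compound symmetry miscovers only if the variance of the change differs by time. Section 9.9 says no PD variability estimates exist, so the documents cannot show that it does. With complete data the point estimates are the cell means under any of these structures.

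The PBV paragraph also asks only for ratios of geometric means, with no interval or level. That stands as a matter of text, but Kenward-Roger degrees of freedom serve only tests and intervals, so an interval is implied, and the HR/BP paragraph promises one outright.

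It is also tempting to say that miscoverage at 24 h would damage the reading of duration of effect. The objectives in Sections 3 and 9.3 attach duration to PVR, which is measured by catheter only to 4.5 h; for PBV they ask only for the effect. The 24 h scan is a listed PBV time point and no more than that.

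Finally, this is a secondary endpoint with no hypotheses (Section 9.8), and Section 9.2 requires changes to the analysis plan to be reported and explained. That limits the priority. It does not justify keeping a term that does nothing and a fallback that contradicts its own paragraph.

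**Conclusion.** The redundancy is certain and follows from the design: one covariance parameter too many in the PBV model as written, and again in the fallback it names. The HR/BP model shares it if its matrix, whose wording is unclear, is read as unstructured over the three times.

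The harm is conditional. It needs a convergence failure, a choice of homogeneous compound symmetry, and variances that differ by time. Given all three, with the 24 h SD at 1.25, 1.5 or 2 times the 1 h SD, nominal 95% coverage at 24 h is roughly 0.90-0.92, 0.86-0.90 or 0.80-0.87, with over-coverage at 1 h. With equal SDs it is 0.95. The SD ratios, the SD pattern between 1 and 24 h, the correlations, the split by dose and complete data are all assumptions. This is a low-to-moderate priority correction.

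**What to change.** In Section 9.6:

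- Delete the random subject term from the PBV model. Delete it from the HR/BP model too if that matrix is meant to be unstructured over 0.5, 4.5 and 24 h, and reword that sentence to say so.
- State whether the PBV matrix is common to all doses or separate by dose, and allow the by-dose version only if every dose group has at least 5 participants.
- Replace the compound-symmetry example with a fixed order: unstructured pooled over doses; then heterogeneous Toeplitz or heterogeneous compound symmetry; then one-sample t intervals for each dose and time, the method already used for PVR.
- State whether PBV results carry a confidence interval, and at what level.

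The cost is SAP wording only. Data collection, sample size and conduct do not change.

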9.7 Interim Analyses

There is no interim analysis involved in this study.

9.8 Multiplicity

Since there are no hypotheses, no adjustments for multiplicity are needed.

9.9 Sample Size and Power Calculations

There are no variability estimates for PK or PD are available for this participant population from which to estimate power or precision. Nevertheless, a sample size of twenty, along with PD evaluations at 2 dose levels, is considered adequate to meet the needs of the study.

10 SUPPORTING DOCUMENTATION AND OPERATIONAL CONSIDERATIONS

10.1 Appendix 1: Regulatory, Ethical, and Study Oversight Considerations

10.1.1 Code of Conduct for Clinical Trials

Merck Sharp and Dohme Corp., a subsidiary of Merck & Co., Inc. (MSD)

Code of Conduct for Interventional Clinical Trials

I. Introduction

A. Purpose

MSD, through its subsidiaries, conducts clinical trials worldwide to evaluate the safety and effectiveness of our products. As such, we are committed to designing, implementing, conducting, analyzing and reporting these trials in compliance with the highest ethical and scientific standards. Protection of participants in clinical trials is the overriding concern in the design of clinical trials. In all cases, MSD clinical trials will be conducted in compliance with local and/or national regulations (eg, International Council for Harmonisation Good Clinical Practice [ICH-GCP]) and in accordance with the ethical principles that have their origin in the Declaration of Helsinki.

B. Scope

Highest ethical and scientific standards shall be endorsed for all clinical interventional investigations sponsored by MSD irrespective of the party (parties) employed for their execution (eg, contract research organizations, collaborative research efforts). This Code is not intended to apply to trials that are observational in nature, or which are retrospective. Further, this Code does not apply to investigator-initiated trials, which are not under the full control of MSD.

II. Scientific Issues

A. Trial Conduct

1. Trial Design

Except for pilot or estimation trials, clinical trial protocols will be hypothesis-driven to assess safety, efficacy, and/or pharmacokinetic or pharmacodynamic indices of MSD or comparator products. Alternatively, MSD may conduct outcomes research trials, trials to assess or validate various endpoint measures, or trials to determine patient preferences, etc.

The design (ie, participant population, duration, statistical power) must be adequate to address the specific purpose of the trial. Participants must meet protocol entry criteria to be enrolled in the trial.

2. Site Selection

MSD selects investigative sites based on medical expertise, access to appropriate participants, adequacy of facilities and staff, previous performance in clinical trials, as well as budgetary considerations. Prior to trial initiation, sites are evaluated by MSD personnel to assess the ability to successfully conduct the trial.

3. Site Monitoring/Scientific Integrity

Investigative trial sites are monitored to assess compliance with the trial protocol and general principles of Good Clinical Practice (GCP). MSD reviews clinical data for accuracy, completeness, and consistency. Data are verified versus source documentation according to standard operating procedures. Per MSD policies and procedures, if fraud, scientific/research misconduct, or serious GCP-noncompliance is suspected, the issues

are investigated. When necessary, the clinical site will be closed, the responsible regulatory authorities and ethics review committees notified.

B. Publication and Authorship

Regardless of trial outcome, MSD commits to publish primary and secondary results of its registered trials of marketed products in which treatment is assigned, according to the prespecified plans for data analysis. To the extent scientifically appropriate, MSD seeks to publish the results of other analyses it conducts that are important to patients, physicians, and payers. Some early phase or pilot trials are intended to be hypothesis-generating rather than hypothesis testing, in such cases, publication of results may not be appropriate since the trial may be underpowered and the analyses complicated by statistical issues such as multiplicity.

MSD's policy on authorship is consistent with the recommendations published by the International Committee of Medical Journal Editors (ICMJE). In summary, authorship should reflect significant contribution to the design and conduct of the trial, performance or interpretation of the analysis, and/or writing of the manuscript. All named authors must be able to defend the trial results and conclusions. MSD funding of a trial will be acknowledged in publications.

III. Participant Protection

A. Ethics Committee Review (Institutional Review Board [IRB]/Independent Ethics Committee [IEC])

All clinical trials will be reviewed and approved by an IRB/IEC before being initiated at each site. Significant changes or revisions to the protocol will be approved by the ethics committee prior to implementation, except changes required urgently to protect participant safety that may be enacted in anticipation of ethics committee approval. For each site, the ethics committee and MSD will approve the participant informed consent form.

B. Safety

The guiding principle in decision-making in clinical trials is that participant welfare is of primary importance. Potential participants will be informed of the risks and benefits of, as well as alternatives to, trial participation. At a minimum, trial designs will take into account the local standard of care.

All participation in MSD clinical trials is voluntary. Participants enter the trial only after informed consent is obtained. Participants may withdraw from an MSD trial at any time, without any influence on their access to, or receipt of, medical care that may otherwise be available to them.

C. Confidentiality

MSD is committed to safeguarding participant confidentiality, to the greatest extent possible. Unless required by law, only the investigator, Sponsor (or representative), ethics committee, and/or regulatory authorities will have access to confidential medical records that might identify the participant by name.

D. Genomic Research

Genomic research will only be conducted in accordance with a protocol and informed consent authorized by an ethics committee.

IV. Financial Considerations

A. Payments to Investigators

Clinical trials are time- and labor-intensive. It is MSD's policy to compensate investigators (or the sponsoring institution) in a fair manner for the work performed in support of MSD trials. MSD does not pay incentives to enroll participants in its trials. However, when enrollment is particularly challenging, additional payments may be made to compensate for the time spent in extra recruiting efforts.

MSD does not pay for participant referrals. However, MSD may compensate referring physicians for time spent on chart review to identify potentially eligible participants.

B. Clinical Research Funding

Informed consent forms will disclose that the trial is sponsored by MSD and that the investigator or sponsoring institution is being paid or provided a grant for performing the trial. However, the local ethics committee may wish to alter the wording of the disclosure statement to be consistent with financial practices at that institution. As noted above, all publications resulting from MSD trials will indicate MSD as a source of funding.

C. Funding for Travel and Other Requests

Funding of travel by investigators and support staff (eg, to scientific meetings, investigator meetings, etc.) will be consistent with local guidelines and practices.

V. Investigator Commitment

Investigators will be expected to review MSD's Code of Conduct as an appendix to the trial protocol, and in signing the protocol, agree to support these ethical and scientific standards.

